## **8.3** Discontinuation of Treatment and Terminations

#### 8.3.1 Discontinuation of Investigational Product

A SI or designee may discontinue the investigational product for a research participant within an RSSP if a medical condition or other situation occurs such that continued intervention would not be in the best interest of the participant. Similarly, a research participant may choose to discontinue the investigational product within an RSSP at any time for any reason. However, the SI or designee will encourage the research participant to follow the SOA under the intent-to-treat principle (ITT) under either the Master Protocol or by continued participation in PPMI. These research participants will be encouraged to follow the study visits, off treatment, up to the Month 24 visit, following the Schedule of Activities. At a minimum, collection of the Primary Endpoints, AEs, Concomitant

Medications, and other outcome measures should be encouraged. If a complete visit schedule is not feasible, at least 24-month visit should be encouraged. Lost to follow-up should be prevented whenever possible.

Upon discontinuation of investigational product, the research participant should return any unused product (if applicable).

For all research participants, the reason for permanent discontinuation of investigational product must be recorded in the CRF. These data will be included in the trial database and reported.

### 8.3.2 Termination of Participation in the RSSP

A research participant may withdraw consent from an individual RSSP at any time, with no justification required for the decision. Upon termination, the research participant should return any unused investigational product (if applicable). The participant will be encouraged to remain in the Master Protocol under the ITT principle, and can be later rescreened for another RSSP as outlined in Section 8.4.

For all research participants, the reason for RSSP termination must be recorded in the P2P CRF. These data will be included in the trial database and reported.

#### **8.3.3** Termination of Participation in the Master Protocol

A research participant may withdraw consent for study participation in the Master Protocol at any time. No justification is required for the decision.

All participants will be encouraged to continue follow up in the PPMI observational study as per PPMI SOA. If a participant terminates from the Master Protocol prior to completing their full follow-up time in an RSSP, they have to be terminated in the RSSP. Relevant visits using PPMI observational study data can be used for the ITT analysis.

For all research participants, the reason for Master Protocol termination must be recorded in the P2P CRF. These data will be included in the trial database and reported.

#### 8.3.4 Termination of the Master Protocol or of the Intervention by the Investigational New Drug (IND) Holder/ Sponsor - MJFF

The IND-holder/Sponsor reserves the right to terminate the overall Master Protocol or any individual regimen at any time. If there are intervention specific criteria for terminating a regimen, they will be detailed in the RSSP.

### 8.4 Screen Failures and Reassignment

Any participant who signs the Master Protocol consent form will be considered enrolled in the Platform Trial. If a participant fails the Master Protocol screening, at a minimum the following information should be captured in the EDC system:

- Demographics (including any prior screening identifiers)
- Reason for screen failure
- Any eligibility criteria that were assessed prior to when the research participant failed to meet an inclusion criterion or met an exclusion criterion.

If a research participant fails to meet a Master Protocol eligibility criterion, then that participant will be considered to have screen failed and encouraged to continue follow up in the PPMI observational study. Research participants may be re-screened for Master Protocol eligibility immediately after resolution of the disqualifying condition. If a participant is re-screened for Master Protocol eligibility, they must complete a full Master Protocol Screening Visit as outlined in the Schedule of Activities. In order to proceed with the Master Protocol, the research participant must qualify for all Master Protocol eligibility requirements. and any additional eligibility requirements for at least one active RSSP.

If a research participant fails Master Protocol screening, participant will be encouraged to continue follow up in the PPMI observational study.

If a research participant who meets Master Protocol eligibility, is assigned to a regimen, and is randomized within that regimen, but their participation in that regimen is discontinued due to screen failure, that participant may have the opportunity to be re-randomized to a different RSSP. The participant will be considered enrolled in the Master Protocol for up to 6 months and during that time able to be randomized to any available RSSP for which they meet initial screening criteria. The research participant must provide written informed re-consent to the Master Protocol and must still meet the Master Protocol inclusion and exclusion eligibility criteria in order to be re-assigned into a different regimen. However, any participants who elect not to consent to their assigned RSSP will not be given the opportunity to be re-randomized. Re-screening for the Master Protocol and potential re-assignment into a different regimen, if available, may also occur due to the following situations:

- An RSSP is stopped early due to concerns about the safety of the intervention.
  - The research participant may be re-screened after 6 months (or longer if required by the RSSP-specific intervention).
- A research participant completes all activities in the assigned RSSP.
  - The research participant may be re-screened 6 months after RSSP completion (or longer if required by the RSSP-specific intervention).
- A research participant is withdrawn due to an adverse event, or is discontinued by the SI.
  - The research participant cannot be considered for rescreening until 24 months after their date of randomization into the original RSSP. They may be re-screened 6 months after their expected 24 month visit in the original RSSP (or longer if required by the RSSP-specific intervention).

### 8.5 Participant Withdrawal

#### 8.5.1. Participant Withdrawal from an RSSP-Specific Protocol

If a participant withdraws consent from an RSSP for personal reasons (e.g., inconvenience of the intervention, mode of administration, required assessments) the participant cannot be re-assigned to a different RSSP. However, the SI or designee will encourage the research participant to remain in the Master Protocol and follow the Master Protocol under the ITT principle. These research participants will be encouraged to follow the study visits, off treatment, up to the Month 24 visit, following the Schedule of Activities as outlined in Section 8.3.1.

#### 8.5.2. Participant Withdrawal from Master Protocol

If a participant chooses to withdraw from the Master Protocol as well as their assigned RSSP, the SI or designee will encourage the participant to maintain enrollment in the PPMI observational study.

# 9. MASTER PROTOCOL SCHEDULE OF ACTIVITIES

This section describes trial procedures that are common to all interventions tested in the P2P Platform Trial as detailed in the Master Protocol. Each RSSP will follow these procedures and may add additional procedures as described in the corresponding RSSP.

No new data or previously collected data will be used until participants sign the Master Protocol Informed Consent Form (ICF).

Once a participant is enrolled in the P2P Master Protocol the P2P SOA (see Table 1) will be followed instead of the PPMI SOA.

## 9.1 Master Protocol Screening Visit

Screening evaluations will occur within 90 days prior to the baseline visit. Screening has been separated into two groups depending on their last PPMI visit and is further defined in the schedule of assessment table. Before any of the screening evaluations are performed for the specific purpose of this Master Protocol, the participant must provide informed consent for this Master Protocol in compliance with Good Clinical Practice (GCP) and IRB requirements. Collection of AE data will begin after the informed consent is signed and will continue until the participant completes their assigned RSSP, 30 days after treatment discontinuation (whichever comes first), or per the defined terms in the RSSP. The screening procedures listed below will be performed and documented to assess whether a participant meets inclusion/exclusion criteria. Scope of activities at the screening visit will depend on the time of the visit in relation to the last PPMI annual visit.

#### \*Group A participants screened into the Master Protocol <6 months from the last PPMI visit \*Group B participants screened into the Master Protocol $\geq$ 6 months from the last PPMI visit

#### Screening/General Activities:

- Obtain written informed consent
- Assess inclusion and exclusion criteria
- DAT SPECT eligibility
- *Demographics collected previously from the PPMI study*
- Obtain Medical and Family History collected previously from the PPMI study
- Socioeconomics collected previously from the PPMI study
- Perform physical examination
- Measure vital signs, including height and weight
- Measure Orthostatic blood pressure

#### Neuro/Motor Assessment:

- Participant motor function questionnaire (group B only)\*
- Freezing and Falls (group B only)\*

- Neurological Exam
- MDS-UPDRS Part Ia
- MDS-UPDRS Part III Hoehn & Yahr
- MDS-UPDRS Ib & Part II
- Modified Schwab & England ADL
- Assess Features of Parkinsonism (group B only)\*
- Other Clinical Features (group B only)\*
- Clinical Diagnosis
- Primary Research Diagnosis

Non-Motor Assessments:

- Administer Olfactory Testing: University of Pennsylvania Smell Identification Test (UPSIT: group B only)\*
- RBD Screening Questionnaire (group B only)\*
- Epworth Sleepiness Scale (group B only)\*
- SCOPA AUT (group B only)\*
- Neuro QoL (group B only)\*

Cognitive & Psychiatric Assessments:

- Montreal Cognitive Assessment
- Clock Drawing (for group B only)\*
- Lexical Fluency (group B only)\*
- Hopkins Verbal Learning Test-Revised (group B only)\*
- Benton Judgment of Line Orientation (group B only)\*
- Modified Semantic Fluency (Animals only) (group B only)\*
- Letter Number Sequencing (group B only)\*
- Symbol Digit Modalities Test (group B only)\*
- Trail Making Test (A and B) (group B only)\*
- Modified Boston Naming Test (group B only)\*
- Cognitive Change
- Cognitive Characterization
- State-Trait Anxiety Inventory for Adults (group B only)\*
- Geriatric Depression Scale
- QUIP (group B only)\*

#### Global Function Assessments (Group B only)\*:

- CGI-S
- PGI-S
- PDAQ-27

P2P-013 Master Protocol V2.0 Version Date: 29Oct2024\_AM1.0 • Novel PROs

Safety Assessments:

- Clinical safety labs
- Perform 12-lead electrocardiogram
- Administer the Columbia-Suicide Severity Rating Scale (C-SSRS) Baseline questionnaire

Biological Sample Collection (Group B only)\*:

- Research samples (blood and urine)
- Lumbar Puncture (LP)
- Skin biopsy

Imaging Activities:

- Collect blood sample for serum pregnancy test (for women of childbearing potential) prior to DAT SPECT Imaging (if applicable)
- Perform Dopamine Transporter SPECT Imaging
- MRI (group B only)\*

#### Medications:

• Review and document concomitant medications

#### Randomization to RSSP:

• Randomization to open RSSP

#### Adverse Events (AE):

- Review and document adverse events related to Master Protocol procedures
- Current medical conditions review
- Report pregnancy

Other Assessments:

• Visit Status (group B only)\*

### 9.2 Baseline/Randomization Visit

The Baseline/Randomization Visit will take place in-person after the Master Protocol Screening Visit. The following procedures will be performed and are listed in the order to be completed:

- Confirm Master Protocol inclusion/exclusion eligibility
- Measure Weight
- Measure Vital signs and Orthostatic Blood Pressure
- Administer Neurological and Motor Assessments including: MDS-UPDRS Part III and Hoehn & Yahr.
- Perform Global Function Assessments including: CGI-S, PGI-S, Novel PRO, PDAQ-27
- Administer the C-SSRS Baseline questionnaire
- Collect research samples (urine and blood)

- Review and document concomitant medications
- Assess any accessible inclusion/ exclusion criteria for eligibility into all available RSSPs. This is done via available data obtained or collected in the Master Protocol Screening visit.
- Randomization to active study drug or placebo
- Assess and document AEs related to Master Protocol procedures
- Assess current medical conditions
- Assess pregnancy status

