### 7.2 Exclusion Criteria

Participants fulfilling any of the following criteria are not eligible for inclusion in this Master Protocol, or able to participate in an RSSP:

- 1. Received any of the drugs associated with symptomatic parkinsonism within 6 months of Randomization Visit (see Appendix 2).
- 2. Received dopaminergic therapy (levodopa or dopamine agonist) for NSD motor syndrome or cholinesterase inhibitors for NSD cognitive syndrome within 90 days prior to or at the time of randomization.
- 3. Any other medical or psychiatric condition or lab abnormality, which in the opinion of the site investigator might preclude Master Protocol participation.
- 4. Individuals taking any of the drugs that might interfere with the DaTscan read out unless they are willing and medically able to hold the medication for at least 5 half-lives before DAT SPECT imaging (see Appendix 1).
- 5. Women may not be pregnant, lactating or planning pregnancy during the Master Protocol.
- 6. Participation in other investigational drug studies less than 30 days prior to screening (unless specified otherwise in the RSSP).
- 7. History or current diagnosis of electrocardiogram (ECG) or cardiac abnormalities indicating significant risk of safety for participants such as:
  - a. Myocardial infarction, unstable angina pectoris, transient ischemic attack, stent placement or coronary artery bypass graft, any of those within 6 months of screening.
  - b. Cardiac failure [New York Heart Association (NYHA) functional class II-IV], stroke or clinically significant uncontrolled arterial hypertension.
  - c. Clinically significant cardiac arrhythmias (e.g., ventricular tachycardia), complete bundle branch block, high-grade AV block (e.g., bifascicular block, Mobitz type II- and third-degree AV block).
  - d. Resting QTcF >450 ms (in males) or >460 ms (in females) and < 300 ms (regardless of sex) at screening or inability to determine the QTcF interval.
  - e. Long QT syndrome, family history of idiopathic sudden death or congenital long QT syndrome.
- 8. Score "yes" on item 4 or item 5 of the Suicidal Ideation section of the C-SSRS, if this ideation occurred in the past 6 months, or "yes" on any item of the Suicidal Behavior section if this behavior occurred in the past 2 years, except for the "Non-Suicidal-Self Injurious Behavior" (item also included in the Suicidal Behavior section).

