## **15.4 Missing Data**

The primary analysis will include all randomized participants analyzed in the treatment group to which they were initially assigned. Thus, a participant who has partial visit data (less than 24 months) may still be included in the primary analyses and it will be critically important to minimize the occurrence of missing data. Obviously, the optimal strategy for dealing with missing data is to make every effort to obtain complete data during the conduct of each RSSP. Our team will work diligently and use a variety of methods to minimize the percentage of missing data in each sub protocol. Nevertheless, there is likely to be a small percentage of missing data. We will employ strategies to mitigate and then assess the impact of missing data within each sub protocol.

To further assess the potential dependence of the results of the primary analysis to these missing values, a series of sensitivity analyses may be conducted as specified within each sub protocol. For participants that do not provide complete data, we will analyze using the following strategies:

- Last Observation Carried Forward: Missing values will be imputed using the participant's last observed data value.
- Multiple Imputation: Two different imputation methods (described below) will be used.
  - Multiple Imputation w/ Treatment-Based Imputation: Under this model, missing data are assumed to follow the same pattern as the respective treatment, age, gender, and baseline value complete data. Missing data will be imputed using a regression approach. If needed, Monte Carlo Markov Chain methodology will be used to impute missing values to obtain a monotone missing data pattern.
  - Pattern-Mixture Model with Placebo-Based Imputation: Under this model, RSSP treatment participants with missing data are assumed to follow the same trajectory as placebo participants. Data from placebo participants only will be used to impute all missing data (from both RSSP treatment and placebo participants) using the full conditional specification regression method.

The results of these analyses will provide valuable information regarding the sensitivity of the findings to the missing data and will be critical in assessing the full value of the RSSP results.

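### The fixed order of Baseline procedures in section 9.2 confirms eligibility before its inputs are collected and reviews current medical conditions only after randomisation, so a new excluding condition can come to light too late

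*Protocol*

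**What the plan says.** Section 9.2 introduces the Baseline procedures with "The following procedures will be performed and are listed in the order to be completed". The other visit lists in section 9 carry no such statement. The list has thirteen steps. It opens with "Confirm Master Protocol inclusion/exclusion eligibility". The C-SSRS is sixth and the concomitant-medication review eighth. The ninth step checks regimen-level criteria using data already obtained at Master Protocol screening. The tenth is "Randomization to active study drug or placebo". Three steps follow it: "Assess and document AEs related to Master Protocol procedures", "Assess current medical conditions" and "Assess pregnancy status".

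Section 7.2 bars anyone who meets an exclusion criterion from the Master Protocol and from a regimen. Exclusion 3 is open-ended: "Any other medical or psychiatric condition or lab abnormality, which in the opinion of the site investigator might preclude Master Protocol participation". Exclusion 7 lists cardiac and cerebrovascular conditions, and exclusion 5 covers pregnancy. Section 9.1 allows screening up to 90 days before Baseline. On the analysis side, section 15.4 states "The primary analysis will include all randomized participants analyzed in the treatment group to which they were initially assigned", and section 15.5 defines the primary population on the same principle.

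**The concern.** A check can prevent an ineligible randomisation only if it is done before randomisation. In the stated order, the one Baseline step devoted to current medical conditions comes afterwards. The one step that confirms Master Protocol eligibility comes before the suicidality and medication data that several criteria need, and it is not repeated.

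At stake are avoidable cases in which a participant already holds an assignment when an excluding condition is noted. The site must then decide about treatment for someone whom section 7.2 says should not be in the regimen, and the primary analysis carries that person in the assigned arm. Keeping such people in the intention-to-treat set is correct. The weakness is a written sequence that can create such cases when a different order of the same steps would not.

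**Working it through.** The question is one of sequence, and the protocol gives no figure to reproduce. The inputs are the order in section 9.2, the Baseline column of Table 1, the screening content in section 9.1, the exclusions in section 7.2, the randomisation rule in section 8.2.1 and the analysis set in sections 15.4 and 15.5.

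**Steps against criteria**

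| Step in 9.2 | Content | Exclusions informed | Before randomisation (step 10)? |
|---|---|---|---|
| 1 | Confirm Master Protocol eligibility | all | yes |
| 6 | C-SSRS | 8 | yes, but after step 1 |
| 8 | Concomitant medications | 1, 2, 4 | yes, but after step 1 |
| 9 | Accessible regimen criteria | regimen-specific | yes, on screening data |
| 11 | AEs related to Master Protocol procedures | none specifically | no |
| 12 | Current medical conditions | 3, 7 | no |
| 13 | Pregnancy status | 5 | no |

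Three of the thirteen steps follow randomisation, and two of those three bear on an exclusion criterion.

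**What else at Baseline could find a new condition?** Table 1 marks inclusion/exclusion review, weight, vital signs with orthostatic blood pressure, and the Part III motor examination. It marks no physical examination, ECG or clinical safety laboratory tests. Those are done at screening, as is a medical-conditions review, but screening may be up to 90 days earlier. The ninth step does not refresh the information, because it relies on screening data. For a cardiac, cerebrovascular or psychiatric event since screening, the medical-conditions review is thus the main listed Baseline check besides whatever the site asks at the first step.

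**Medication timing.** Exclusion 2 in section 7.2 runs up to the time of randomisation, so it needs current medication data. The medication review precedes randomisation and can stop it, but no later step returns to Master Protocol eligibility once that information is in hand.

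**Size.** The documents give no rate of newly acquired excluding conditions, so the number affected cannot be derived. As an illustration only, assume that a fraction f of participants acquire one in the gap, that every other check misses all of them, and that those in the active arm go untreated and progress like placebo. With 125 active participants per regimen and a true 40% slowing:

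- Number affected in the active arm = 125 × f. At f = 1%, 125 × 0.01 = 1.25; at f = 5%, 125 × 0.05 = 6.25.
- Diluted slowing = 40% × (1 − f). At f = 1% this is 39.6%; at f = 5% it is 38.0%.
- Section 15.3 gives 91% power when both endpoints slow by 40% and 84% when both slow by 35%. Linear interpolation at 39.6% gives 91 − (0.4/5) × 7 = 90.4%. At 38.0% it gives 91 − (2/5) × 7 = 88.2%.

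The 1–5% range is an assumption, and complete failure of the other checks is a worst case. Real losses would be smaller.

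**The case against.** The strongest reply is that eligibility is already gated. The first step of the visit confirms it, and Table 1 marks inclusion/exclusion review at Baseline. Confirming exclusions 3, 5 and 7 properly means asking about intervening events then. Section 8.2.1 allows within-regimen randomisation only once the additional regimen criteria are met, after a regimen-specific screening visit whose content lies in sub-protocols not shown here. Section 16.5.3 makes the site investigator answerable for enrolling only eligible participants. The end of the 9.2 list also follows the row order of Table 1, where the medical-conditions review sits in the adverse-event block and recurs at every visit. That suggests routine data capture and a drafting carry-over, not a decision to defer eligibility checks.

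Much of this stands. A reader might infer that the order causes ineligible people to be randomised. The documents do not support that, because a careful site can catch a new condition at the first step. Nor do they show that such a person would receive study drug: section 9.2 lists no dosing step, and section 8.3.1 allows product to be discontinued. The adverse-event step covers only procedure-related events and should not be counted as an eligibility check. Pregnancy is nearly moot with entry at age 60 or older and a serum test at screening where applicable. The C-SSRS and medication review do precede randomisation.

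The reply does not explain why a list declared to be in order of completion puts the only dedicated medical-conditions step where it cannot prevent assignment, or why eligibility is not confirmed again once the visit's own data are available.

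**Conclusion.** The point holds as a sequencing defect. Followed literally, section 9.2 can allow an avoidable randomisation of a participant whose excluding condition arose after screening and was not picked up at the first step. It does not show that this will happen, or how often.

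The number affected is probably small. Even the worst-case illustration at an assumed 5% moves a 40% slowing only to 38.0% and costs just under 3 points of power. At 1% the cost is about half a point. With the other checks working, I would treat the effect on power as negligible. A reader might also infer that retaining these participants biases the primary analysis. It does not: the condition predates assignment, so it is not a consequence of treatment, and analysis as randomised is standard. The reason to act is participant safety and a cleaner randomised set, at almost no cost.

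The conclusion rests on reading the stated order as binding and on Table 1 for Baseline content. A sub-protocol that repeats the medical review shortly before randomisation would reduce the practical risk, but the text of section 9.2 would still need correcting.

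**What to change.** In section 9.2:

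1. Move the current-medical-conditions step and, where applicable, the pregnancy-status step ahead of randomisation.
2. Place the Master Protocol eligibility confirmation directly before randomisation, after the C-SSRS and medication review. If the sponsor wants an early check as well, keep it at the start and repeat it there.
3. Leave the procedure-related adverse-event step where it is, if preferred, since it is not an eligibility check.

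The Baseline worksheet should be changed to match. The cost is re-ordering, and at most repeating, existing steps in an amendment. No assessment, visit or participant is added, and the randomisation scheme and analysis are unchanged.
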